### 6.15.2. Adverse Events

Adverse events are recorded in the eCRFs. Each AE will be coded to system organ class (SOC) and preferred term (PT) using the Medical Dictionary for Regulatory Activities (MedDRA) version that is current at the time of database lock. Severity of AEs is recorded as mild, moderate, or severe.

A TEAE is defined as an event that either first occurred or worsened in severity after the first dose of study treatment and on or prior to the last visit date during the analysis period. The analysis period is defined as the treatment period plus up to 30 days off-drug follow-up time.

Adverse events are classified based upon the MedDRA PT. The MedDRA Lowest Level Term (LLT) will be used in defining which events are treatment-emergent. The maximum severity for each LLT during the baseline period up to first dose of the study medication will be used as baseline. If an event with missing severity is preexisting during the baseline period, and persists during the treatment period, then the baseline severity will be considered mild for determining treatment-emergence (that is, the event is treatment-emergent if the severity is coded moderate or severe postbaseline and not treatment-emergent if the severity is coded mild postbaseline). If an event occurring postbaseline has a missing severity rating, then the event is considered treatment-emergent unless the baseline rating is severe, in which case the event is not treatment-emergent. The day and time for events where onset is on the day of the first dose of study treatment will both be used to distinguish between pretreatment and posttreatment to derive treatment-emergence. Should there be insufficient data for AE start date to make this comparison (for example, the AE start year is the same as the treatment start year, but the AE start month and day are missing), the AE will be considered treatment-emergent.

In general, summaries will include the number of patients in the safety population (N), frequency of patients reporting the event (n), and relative frequency (that is, percentage;  $n/N*100$ ). For any events that are gender-specific based on the displayed PT, the denominator used to compute the percentage will only include patients from the appropriate gender.

In an overview table, the number and percentage of patients in the safety population who experienced death, an SAE, any TEAE, discontinuation from the study due to an AE, permanent discontinuation from study drug due to an AE, or a severe TEAE will be summarized by treatment group.

The number and percentage of patients with TEAEs will be summarized by treatment group in 2 formats by MedDRA PT:

- nested within SOC with decreasing frequency in SOC, and events ordered within each SOC by decreasing frequency in the baricitinib 4-mg group;
- with events ordered by decreasing frequency in the baricitinib 4-mg group.

#### **6.15.2.1. Common Adverse Events**

Common TEAEs are defined as TEAEs that occurred in  $\geq 2\%$  (before rounding) of patients in any treatment group including placebo. The number and percentage of patients with common TEAEs will be summarized by treatment using MedDRA PT ordered by decreasing frequency in the baricitinib 4-mg group.

The number and percentage of patients with TEAEs will be summarized by maximum severity by treatment using MedDRA PT ordered by decreasing frequency in the baricitinib 4-mg group for the common TEAEs. For each patient and TEAE, the maximum severity for the MedDRA level being displayed is the maximum postbaseline severity observed from all associated LLTs mapping to that MedDRA PT.

#### **6.15.2.2. Serious Adverse Event Analyses**

Consistent with the International Conference on Harmonisation (ICH) E2A guideline (1994) and 21 Code of Federal Regulations (CFR) 312.32 (a) (2010), a SAE is any AE that results in any one of the following outcomes:

- death
- initial or prolonged inpatient hospitalization
- a life-threatening experience (that is, immediate risk of dying)
- persistent or significant disability/incapacity
- congenital anomaly/birth defect

The number and percentage of patients who experienced any SAE will be summarized by treatment using MedDRA PT nested within SOC. Events will be ordered by decreasing frequency in the baricitinib 4-mg group within decreasing frequency in SOC. The SAEs will also be summarized by treatment using MedDRA PT without SOC.

An individual listing of all SAEs will be provided. A listing of deaths, if any, regardless of when they occurred during the study, will also be provided.

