9.2.1. Serious Adverse Events

An SAE is any AE from this study that results in 1 of the following outcomes:

- death
- initial or prolonged inpatient hospitalization
- a life-threatening experience (i.e., immediate risk of dying)
- persistent or significant disability/incapacity
- congenital anomaly/birth defect
- important medical events that may not be immediately life threatening or result in death or hospitalization but may jeopardize the patient or may require intervention to prevent 1 of the other outcomes listed in the definition above. Examples of such medical events include allergic bronchospasm requiring intensive treatment in an emergency room or at home, blood dyscrasias or convulsions that do not result in inpatient hospitalization, or the development of drug dependency or drug abuse.

All AEs occurring after signing the ICF are recorded in the eCRF and assessed for serious criteria. The SAE reporting to the sponsor begins after the patient has signed the ICF and has received investigational product. However, if an SAE occurs after signing the ICF, but prior to receiving investigational product, the SAE should be reported to the sponsor as per SAE reporting requirements and timelines if it is considered reasonably possibly related to study procedure.

Study site personnel must alert Lilly or its designee of any SAE within 24 hours of investigator awareness of the event via a sponsor-approved method (e.g. investigator space portal, telephone, or fax). If alerts are issued via telephone, they are to be immediately followed with official notification on study-specific SAE forms. This 24-hour notification requirement refers to the initial SAE information and all follow-up SAE information. Patients with a serious hepatic AE should have additional data collected using the hepatic safety eCRF. Investigators can contact the sponsor via telephone at any time using the qualified medical personnel or Lilly affiliate medical contact details which are provided in the site study file.

Pregnancy (during maternal or paternal exposure to investigational product) does not meet the definition of an AE. However, to fulfill regulatory requirements, any pregnancy should be reported following the SAE process to collect data on the outcome for both mother and fetus.

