#### **6.15.5.6. Infections**

Infections will be defined using all the PTs from the Infections and Infestations SOC as defined in MedDRA. Serious infection will be defined as all the infections that meet the SAE criteria.

The number and percentage of patients with TEAEs of infections, serious infections, and infections resulting in permanent study drug discontinuation will be summarized by treatment group using MedDRA PTs. The proportion of patients developing skin infections requiring antibiotic treatment by Week 16 will also be summarized on the overview of infections table.

The number and percentage of patients with TEAEs of infections by maximum severity will be summarized by treatment group using MedDRA PTs.

Treatment-emergent infections will be reviewed in context of other clinical and laboratory parameters via a listing (details see Compound level safety standards).

The TEAE infections will be further analyzed in terms of potential opportunistic infection, herpes zoster and herpes simplex. Summary of HBV DNA monitoring results and association between infection and neutropenia/lymphopenia will also be provided in the context of infections.

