### **6.21. Clinical Trial Registry Analyses**

Additional analyses will be performed for the purpose of fulfilling the Clinical Trial Registry (CTR) requirements.

Analyses provided for the CTR requirements include a summary of AEs, provided as a dataset which will be converted to an XML file. Both SAEs and ‘Other’ AE are summarized: by treatment group, by MedDRA PT.

- An AE is considered ‘Serious’ whether or not it is a TEAE.
- An AE is considered in the ‘Other’ category if it is both a TEAE and is not serious. For each SAE and ‘Other’ AE, for each term and treatment group, the following are provided:
  - the number of participants at risk of an event
  - the number of participants who experienced each event term
  - the number of events experienced.
- Consistent with www.ClinicalTrials.gov requirements, ‘Other’ AEs that occur in fewer than 5% of patients/subjects in every treatment group may not be included if a 5% threshold is chosen (5% is the minimum threshold).
- AE reporting is consistent with other document disclosures for example, the CSR, manuscripts, and so forth.

Similar methods will be used to satisfy the European Clinical Trials Database (EudraCT) requirements.

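### SAP 6.15.2.2 defines a serious adverse event by five outcomes and omits the protocol's sixth, important medical events; SAP 6.15.5.6 carries the shorter list into serious infections

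*SAP*

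**What the plan says.** Protocol 9.2.1 opens its definition with "An SAE is any AE from this study that results in 1 of the following outcomes" and gives six items. The sixth is "important medical events that may not be immediately life threatening or result in death or hospitalization but may jeopardize the patient", or that may call for intervention to prevent one of the other outcomes. Its examples include "blood dyscrasias or convulsions that do not result in inpatient hospitalization, or the development of drug dependency or drug abuse". The same section says how seriousness is captured, "All AEs occurring after signing the ICF are recorded in the eCRF and assessed for serious criteria", and sets the reporting duty: "Study site personnel must alert Lilly or its designee of any SAE within 24 hours of investigator awareness of the event".

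SAP 6.15.2.2 states its own definition, "a SAE is any AE that results in any one of the following outcomes", followed by five items. It then specifies the SAE tables by treatment and the SAE listing.

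Two later SAP sections depend on seriousness. In 6.15.5.6: "Serious infection will be defined as all the infections that meet the SAE criteria". In 6.21, on registry reporting: "An AE is considered in the ‘Other’ category if it is both a TEAE and is not serious".

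**The concern.** The analysis document and the protocol give different definitions of the same safety endpoint, and the SAP's is the narrower one. Sites must report to the sponsor under six criteria, while the SAP describes tables built on five. An event that is serious only because it is an important medical event could be reported to the sponsor as an SAE within 24 hours and yet, on a literal reading of the SAP, not appear in the SAE table. Infections are a protocol adverse event of special interest, so the inherited definition of serious infection matters as well. Even if programming does the right thing, a reader of the SAP could not tell which definition the reported counts follow.

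**Working it through.** The plan gives no expected SAE rate or other figure to reproduce. The check is a comparison of the two lists, a trace of where the SAP uses its list, and the scale of the effect per patient.

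**1. The two lists, item by item**

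| Outcome | Protocol 9.2.1 | SAP 6.15.2.2 |
|---|---|---|
| Death | yes | yes |
| New or extended inpatient stay | yes | yes |
| Immediate threat to life | yes | yes |
| Lasting or significant disability | yes | yes |
| Birth defect | yes | yes |
| Important medical events | yes | **no** |
| Count | 6 | 5 |

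The difference is 6 − 5 = 1 item. The five shared items stand in the same order. The SAP list is not offered as a set of examples, and its section refers neither to protocol 9.2.1 nor to the eCRF assessment. SAP 6.15.2 says that AEs are recorded in the eCRFs and covers their coding and severity, but not the source of the seriousness classification. No other SAP section restores the missing item.

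**2. Where the definition is used**

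- The SAE tables and the SAE listing are specified in 6.15.2.2 itself.
- The overview table in 6.15.2 counts patients with an SAE.
- Serious infection in 6.15.5.6 is tied to the SAE criteria. The only such criteria written in the SAP are the five in 6.15.2.2.
- The registry split in 6.21 turns on seriousness, but that section does not cite 6.15.2.2.

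**3. Scale**

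Input: 100 patients planned per arm (SAP 5.1; Protocol 5.1).

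Suppose k patients in an arm have SAEs that meet only the sixth outcome. Under the five-item list, that arm's SAE incidence falls by k / 100. For k = 1 this is 1 / 100 = 1 percentage point. The safety population may be slightly smaller than 100 per arm, hence *about* 1 point. The same arithmetic applies to the serious-infection row, with k counting patients whose only serious infections meet only the sixth outcome.

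In terms of events, if a share q of all SAEs meets only the sixth outcome, tables built to the SAP list omit the share q. The documents give neither q nor an expected SAE rate. As an assumption q can lie anywhere from 0 to 100%, so the total effect cannot be computed.

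**4. The two ways the tables could be built**

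- From the SAP wording: the omission in step 3 occurs whenever k is at least 1.
- From the eCRF seriousness assessment made under protocol 9.2.1: nothing is omitted, and the fault is confined to the SAP text.

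The SAP does not say which applies.

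**The case against.** The strongest reply is that the SAP list is an incomplete restatement that nobody will program. The protocol has every AE assessed for seriousness in the eCRF, and the SAP takes its AEs from the eCRF. Section 6.15.2.2 contains no derivation and no step that reclassifies an event the investigator called serious. Elsewhere the SAP treats seriousness as an attribute of the recorded event: it is an item in the herpes zoster and herpes simplex summaries and in the listings of adjudicated cardiovascular and thromboembolic events. On this reading the counts are correct.

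Much of that stands, and it makes the harm conditional. A reader might infer that the SAE rate will be understated. The documents do not show this, because no passage plans to override the recorded assessment. The reply does not remove the point, however. The SAP never names the recorded assessment as its source, and under the heading that governs the SAE analyses it states a different rule. The compound level safety standards, which the SAP uses for several other safety definitions, are not cited in 6.15.2.2 and cannot be checked here.

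Three further inferences go too far:

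- *That signals for the named risks would be lost.* Positively adjudicated thromboembolic events (6.15.5.8), malignancies (6.15.5.10), herpes zoster (6.15.5.6) and graded haematological changes (6.15.5.2) each have their own summaries, which do not depend on the SAE definition. Such events could lose only the serious label.
- *That SAE counts should agree with adjudicated events.* Adjudication is not restricted to serious events, so the counts need not match under either definition.
- *That the registry will move such events to the non-serious category.* Section 6.21 does not cite 6.15.2.2, and it asks for consistency with other disclosures such as the study report. The risk is ambiguity rather than a planned reclassification.

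**Conclusion.** The inconsistency is certain: five outcomes against six, with important medical events missing from the SAP and the shorter list passed on to serious infections. Followed as written, it is a wrong rule and not merely a missing detail.

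The consequence for the counts is conditional on two things: that the tables are built to the SAP list and not to the eCRF assessment, and that at least one event is serious solely by the sixth outcome. If both hold, each affected patient costs that arm about 1 percentage point of incidence at about 100 per arm. If either fails, the counts are right. Where the eCRF assessment is the source, the SAP still misdescribes the definition behind its tables. The overall size is not computable from the documents and may be zero.

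No efficacy result, alpha allocation or sample size is touched. It should be corrected, but it does not threaten the trial's main conclusions.

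**What to change.** In SAP 6.15.2.2, do one of the following:

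- add the sixth outcome, so that the list matches protocol 9.2.1; or
- replace the list with a statement that an SAE is any AE assessed as serious in the eCRF under protocol 9.2.1.

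The second is preferable because it also names the data source. In either case, state that the SAE criteria in 6.15.5.6 and the term serious in 6.21 refer to the same assessment.

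The cost is one or two lines of SAP text. No new data are needed. The SAE and serious-infection counts stay the same if the eCRF assessment was already going to be used, and otherwise may rise slightly.

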#### **6.15.2.3. Other Significant Adverse Events**

Other significant AEs to be summarized will provide the number and percentage of patients who:

- permanently discontinued study drug because of an AE or death

- temporarily interrupted study drug because of AE

by treatment using MedDRA PT nested within SOC. Events will be ordered by decreasing frequency in the baricitinib 4-mg group within decreasing frequency in SOC.

A summary of temporary interruptions of study drug will also be provided, showing the number of patients who experienced at least one temporary interruption and the number of temporary interruptions per patient with an interruption. Further, the duration of each temporary interruption (in days), the cumulative duration of dose interruption (in days) using basic descriptive statistics and the reason for dose interruption will be provided.

A listing of all AEs leading to permanent discontinuation from the study drug or from the study will be provided. A listing of all temporary study drug interruptions, including interruptions for reasons other than AEs, will be provided.

#### **6.15.2.4. Criteria for Notable Patients**

Patient narratives will be provided for all patients who experience certain “notable” events prior to data cutoff for the submission. See compound level safety standards for list of criteria.

### **6.15.3. Clinical Laboratory Evaluation**

For the categorical laboratory analyses (shift and treatment emergent), the analysis period is defined as the treatment period plus up to 30 days off-drug follow-up time. The analysis period for the continuous laboratory analyses (e.g., change from baseline by time point) is defined as the treatment period excluding off-drug follow-up time.

All laboratory tests will be presented using the International System (SI) and US conventional (CN) units. The performing central laboratory reference ranges will be used to define the low and high limits. Results pertaining to the 4 key hepatic laboratory assessments (alanine aminotransferase [ALT], aspartate aminotransferase [AST], total bilirubin, and alkaline phosphatase [ALP]) will be included as a separate analysis to address the risk of liver injury as a special safety topic (see Section 6.15.5.1).

There is one special circumstance for laboratory values to be derived based on regularly scheduled, protocol-specified analytes. The low-density lipoprotein/high-density lipoprotein (LDL/HDL) ratio will be derived as the ratio of LDL cholesterol to HDL cholesterol. There are no central lab reference ranges for the LDL/HDL ratio.

The following will be conducted for the laboratory analytes collected quantitatively:

- **Box plots:** Values at each visit (starting from randomization) and change from last baseline to each visit and to last postbaseline measure will be displayed in box plots for patients who have both a baseline and at least 1 postbaseline visit. The last non-missing observation in the treatment period will be used as the last observation. Individual measurements outside of reference limits will also be displayed using distinct symbols overlaying the box plot. Original-scale data will be used for the display but for some analytes (for example, immunoglobulins) a logarithmic scale may be used to aid in viewing the measures of central tendency and dispersion. Unplanned measurements will

be excluded. Descriptive summary statistics will be included below the box plot along with p-values resulting from between treatment comparison in change from last baseline to last observation. An ANCOVA model with explanatory term for treatment and the baseline value as a covariate will be used. These box plots will be used to evaluate trends over time and to assess a potential impact of outliers on central tendency summaries.

- **Treatment-emergent high/low analyses:** The number and percentage of patients with treatment-emergent high and low laboratory results at any time will be summarized by treatment group. Planned and unplanned measurements will be included. A treatment-emergent **high** result is defined as a change from a value less than or equal to the high limit at all baseline visits to a value greater than the high limit at any time during the treatment period. A treatment-emergent **low** result is defined as a change from a value greater than or equal to the low limit at all baseline visits to a value less than the low limit at any time during the treatment period. The Fisher's exact test will be used for the treatment comparisons. Number at risk (NAR) for the treatment-emergent high result is defined as the number of patients with a value less than or equal to the high limit at all baseline visits. NAR for the treatment-emergent low result is defined as the number of patients with a value greater than or equal to the low limit at all baseline visits for the treatment-emergent low result.

A listing of abnormal findings will be provided for laboratory analyte measurements, including qualitative measures. The listing will include but not limited to patient ID, treatment group, laboratory collection date, analyte name, and analyte finding. If needed by the safety physician/scientist, for analytes measured qualitatively, the number and percentage of patients with treatment-emergent abnormal laboratory results at any time will be summarized by treatment. Planned and unplanned measurements will be included. A treatment-emergent abnormal result is defined as a change from normal at all baseline visits to abnormal at any time postbaseline.

Note that additional analyses of certain laboratory analytes will be discussed within sub-sections of Section 6.15.5 pertaining to Special Safety topics (Section 6.15.5.1 for hepatic analytes, Section 6.15.5.2 for analytes related to hematological changes, Section 6.15.5.3 for analytes related to lipids, Section 6.15.5.4 for analytes related to renal function, and Section 6.15.5.5 for CPK).

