- d TB test(s) including PPD, QuantiFERON®-TB Gold, and T SPOT®. See Exclusion Criterion [39] for description of TB testing. In countries where the QuantiFERON-TB Gold test or T-SPOT is available, either test may be used instead of the PPD TB test. The QuantiFERON-TB Gold test may be performed centrally (recommended/preferred) or locally; the T-SPOT must be performed locally. (Note: Exception: Patients with a history of active or latent TB who have documented evidence of appropriate treatment, have no history of re-exposure since their treatment was completed, and have a screening chest x-ray with no evidence of active TB may be enrolled if other entry criteria are met. Such patients would not be required to undergo the protocol-specific TB testing but must have a chest x-ray at screening.)
- e If PPD testing was chosen to test for TB, then the patient must return and have the PPD test read 48 to 72 hours after Visit 1 (post-PPD).
- f ePRO devices will need to be collected from screen fail patients.
- g For patients not entering Study JAHN, their JAIY patient diary will continue to be dispensed at the final visit and returned at Visit 801.
- h Only as required based on clinical symptoms.
- i The following measures (POEM, DLQI, EQ-5D-5L, WPAI-AD, PIQ, PROMIS, Neuro-QoL, and PBI) should be completed prior to any clinical assessments being performed on days when study visits occur.
- j These will be conducted in the countries where translations are available.
- k Suicidal ideation and behavior subscales excerpt—Adapted for the assessment of 11 preferred ideation and behavior categories.
- l The Self-Harm Follow-up Form is only required if triggered by the Self-Harm Supplement Form.
- m Clinical chemistry will include the following value calculated by the central laboratory from serum creatinine: estimated glomerular filtration rate (eGFR, calculated using the Chronic Kidney Disease Epidemiology Collaboration [CKD-EPI] Creatinine 2009 equation).
- n Fasting lipid profile: Patients should not eat or drink anything except water for 12 hours prior to sample collection. If a patient attends these visits in a nonfasting state, this will not be considered a protocol violation.
- o Only required for patients completing an ETV prior to completion of Visit 7 (Week 12).

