#### **6.15.4. Vital Signs and Other Physical Findings**

For the treatment-emergent categorical analyses (shift and treatment emergent), the analysis period is defined as the treatment period plus up to 30 days off-drug follow-up time. The analysis period for the continuous analyses (e.g., change from baseline by time point) is defined as the treatment period excluding off-drug follow-up time.

Vital signs and physical characteristics include systolic blood pressure (SBP), diastolic blood pressure (DBP), pulse, weight, and BMI. Original-scale data will be analyzed. When these parameters are analyzed as continuous numerical variables, unplanned measurements will be

excluded. When these parameters are analyzed as categorical outcomes and/or treatment-emergent abnormalities, planned and unplanned measurements will be included.

The planned analyses described for the laboratory analytes in Section 6.15.3 will be used to analyze the vital signs and physical characteristics.

Table JAIY.6.8 defines the low and high baseline values as well as the criteria used to define treatment-emergence based on post-baseline values. The blood pressure and pulse rate criteria are consistent with the document *Selected Reference Limits for Pulse/Heart Rate, Arterial Blood Pressure (Including Orthostasis), and Electrocardiogram Numerical Parameters for Use in Analyses of Phase 2-4 Clinical Trials Version 1.3* approved on April 29, 2015 as recommended by the Lilly Cardiovascular Safety Advisory Committee (CVSAC).

**Table JAIY.6.8. Categorical Criteria for Abnormal Treatment-Emergent Blood Pressure and Pulse Measurement, and Categorical Criteria for Weight Changes for Adults**

Parameter (Units of Measure)	Low	High
Systolic Blood Pressure (mm Hg)	≤90 (low limit) and decrease from lowest value during baseline ≥20 if >90 at each baseline visit	≥140 (high limit) and increase from highest value during baseline ≥20 if <140 at each baseline visit
Diastolic Blood Pressure (mm Hg)	≤50 (low limit) and decrease from lowest value during baseline ≥10 if >50 at each baseline visit	≥90 (high limit) and increase from highest value during baseline ≥10 if <90 at each baseline visit
Pulse (beats per minute)	<50 (low limit) and decrease from lowest value during baseline ≥15 if ≥50 at each baseline visit	>100 (high limit) and increase from highest value during baseline ≥15 if ≤100 at each baseline visit

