### 6.15.5.1. Abnormal Hepatic Tests

Analyses for abnormal hepatic tests will involve 4 laboratory analytes: ALT, AST, total bilirubin, and ALP. In addition to the analyses described in Section 6.15.3, this section describes specific analyses for this topic.

First, the number and percentage of patients with the following abnormal elevations in hepatic laboratory tests at any time will be summarized between treatment groups:

- The percentages of patients with an ALT measurement  $\geq 3\times$ ,  $5\times$ , and  $10\times$  the central laboratory upper limit of normal (ULN) during the treatment period will be summarized for all patients with a postbaseline value and for subsets based on various levels of baseline.
  - The analysis of  $3\times$  ULN will contain 4 subsets: patients whose non-missing maximum baseline value is  $\leq 1\times$  ULN, patients whose maximum baseline is  $>1\times$  ULN but  $<3\times$  ULN, patients whose maximum baseline value is  $\geq 3\times$  ULN, and patients whose baseline values are missing.
  - The analysis of  $5\times$  ULN will contain 5 subsets: patients whose non-missing maximum baseline value is  $\leq 1\times$  ULN, patients whose maximum baseline is  $>1\times$  ULN but  $<3\times$  ULN, patients whose maximum baseline is  $\geq 3\times$  ULN but  $<5\times$  ULN, patients whose maximum baseline value is  $\geq 5\times$  ULN, and patients whose baseline values are missing.
  - The analysis of  $10\times$  ULN will contain 6 subsets: patients whose non-missing maximum baseline value is  $\leq 1\times$  ULN, patients whose maximum baseline is  $>1\times$  ULN but  $<3\times$  ULN, patients whose maximum baseline is  $\geq 3\times$  ULN but  $<5\times$  ULN, patients whose maximum baseline is  $\geq 5\times$  ULN but  $<10\times$  ULN, patients whose maximum baseline value is  $\geq 10\times$  ULN, and patients whose baseline values are missing.
- The percentages of patients with an AST measurement  $\geq 3\times$ ,  $5\times$ , and  $10\times$  the central laboratory ULN during the treatment period will be summarized for all patients with a postbaseline value and for subsets based on various levels of baseline. Analyses will be constructed as described above for ALT.

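### The number at risk for treatment-emergent high/low laboratory results is set by baseline values alone, so patients with no later value count as event-free; the dilution is minor and most plausible for lipids

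*SAP*

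**What the plan says.** SAP 6.15.3 defines the denominator of the treatment-emergent high table by baseline alone: "Number at risk (NAR) for the treatment-emergent high result is defined as the number of patients with a value less than or equal to" a cut-off, which is the upper limit and must hold at every baseline visit. For the low table, "NAR for the treatment-emergent low result is defined as the number of patients with a value greater than or equal to the low limit", again checked at every baseline visit. Neither sentence asks for a later value. The event does, because the patient must move from within the limit "to a value greater than the high limit at any time during the treatment period". On the comparison of arms the section says: "The Fisher's exact test will be used for the treatment comparisons".

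Elsewhere the SAP does ask for a later value. In SAP 6.15.5.1 the ALT and AST threshold percentages "will be summarized for all patients with a postbaseline value and for subsets based on various levels of baseline", and the bilirubin and ALP percentages carry the same restriction. The box plots in 6.15.3 are for "patients who have both a baseline and at least 1 postbaseline visit".

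SAP 6.2.1 does not supply the missing condition. Its default for incidence-based safety endpoints is the whole safety population unless a section states otherwise. That population leaves out only patients who were never dosed and those lost to follow-up at the first postbaseline visit. SAP 6.15.4 inherits the method: "The planned analyses described for the laboratory analytes in Section 6.15.3 will be used to analyze the vital signs and physical characteristics".

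**The concern.** A patient whose baseline is within limits and who has no later value for an analyte has an unknown outcome. The stated rule treats that patient as a known non-event. This pulls the percentage down. If the untested share differs between arms, it also shifts the comparison of each dose with placebo: more untested patients on baricitinib would hide a signal, and more on placebo would exaggerate one. Lipids matter here because SAP 6.15.5.3 makes them a special safety topic and refers back to 6.15.3 for their analysis.

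**Working it through.** The documents state no untested share and no expected laboratory rate, so there is no figure of the plan's to reproduce on this point.

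**1. Who can be in the denominator without a value**

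Inputs:
- Protocol Schedule of Activities: chemistry and hematology at Weeks 4, 8, 12, 16/ET and Visit 801; lipids at Week 12, at an early termination visit (ETV) that precedes Week 12 (footnote o), and at Visit 801.
- SAP 6.15.3: the analysis period for categorical laboratory analyses is treatment plus up to 30 days off drug.
- SAP 6.15: follow-up data run up to 30 days after the last dose, regardless of study period.

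I read these together as a 30-day clock that starts at the last dose.

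- *Chemistry and hematology.* The Week 4 visit is Day 28 ± 2, so at the latest Day 30. Even a patient who took only the first dose is then at most 30 days off drug, and that sample counts. To be untested, a patient must leave before Week 4 and also have no ETV sample, no Visit 801 sample within 30 days and no unscheduled draw.
- *Lipids.* The Week 12 visit is Day 84, and 84 - 30 = 54. With the ± 4 day tolerance the cut-off lies between Day 50 and Day 58. A patient who stops drug before about Day 54 and remains in the study, as Protocol 5.1.2 and 8.1.2 ask, has no ETV at that point. Protocol 5.1.3 requires no separate Visit 801 once such a patient has been off drug for more than 28 days, and footnote a to the schedule allows it to be combined with Visit 8. At Week 16 that patient is at least 112 - 54 = 58 days off drug. Without an unscheduled test there is no lipid value in the window, yet the patient stays in the number at risk. No visit need be missed.
- *Blood pressure and pulse.* These are measured at every visit from Week 1, so almost no one is untested. The weight criteria in SAP 6.15.4 have no in-range baseline condition.

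**2. Size of the dilution**

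Let r be the rate among re-tested patients and m the untested share of the number at risk. Reported rate = r × (1 - m). Values of m are assumptions.

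| r | m = 2% | m = 5% | m = 10% |
|---|---|---|---|
| 5% | 4.9% | 4.75% | 4.5% |
| 10% | 9.8% | 9.5% | 9.0% |

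**3. Effect on the comparison**

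Reported rate ratio ÷ true rate ratio = (1 - m on baricitinib)/(1 - m on placebo).

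- Equal shares leave the ratio unchanged. At m = 2% in both arms, 15% vs 5% reads 14.7% vs 4.9%: a difference of 9.8 points instead of 10.0.
- 10% on baricitinib, 2% on placebo: 0.90/0.98 = 0.918, so the signal is muted.
- 2% on baricitinib, 10% on placebo: 0.98/0.90 = 1.089, so it is inflated.

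Illustrative counts, taking 100 patients per arm as within limits at baseline:

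| Untested (baricitinib, placebo) | Stated rule | Re-tested only |
|---|---|---|
| 10, 2 | 12/100 vs 4/100, Fisher p = 0.065 | 12/90 vs 4/98, p = 0.034 |
| 2, 10 | 18/100 vs 9/100, p = 0.097 | 18/98 vs 9/90, p = 0.144 |
| 5, 5 | 15/100 vs 5/100, p = 0.032 | 15/95 vs 5/95, p = 0.031 |

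**The case against.** The strongest reply is that the plan already leaves few patients untested. Dosed patients who leave the study early must have an ETV and return for Visit 801, and all three panels are scheduled there. Visit 801 falls 28 ± 4 days after the last dose, largely inside the 30-day window. Unplanned measurements count. Patients lost to follow-up at the first postbaseline visit are already excluded. Footnote o is itself a safeguard, since it asks for a lipid sample at an ETV before Week 12. These tests lie outside the multiplicity scheme, so no confirmatory claim depends on them. All of this stands, and it is why the size is probably small for chemistry and hematology. It does not close the lipid case above, because that patient has not left the study.

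The box plots are also a weak contrast, since a change from baseline needs both values in any case. The hepatic rule is the real one.

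A reader might infer that abnormality rates are understated in every arm, or that the Fisher comparisons are distorted. The documents do not support that. They give no untested share, and with no untested patients there is no effect. Even assumed lipid shares of 15% on placebo and 8% on baricitinib, at a true 20%, give 0.20 × 0.85 = 17.0% vs 0.20 × 0.92 = 18.4%. On about 17/100 vs 18/100, Fisher p = 1.0. A shift across 0.05 needs unequal shares and a result already near the line. Nor do the first routine samples at Week 4 and Week 12 prove a gap by themselves, given the ETV and Visit 801.

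The compound-level safety standards that the SAP cites are not among the documents. They may add the condition, but the explicit definition in 6.15.3 does not.

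**Conclusion.** The point holds as a minor defect of definition. The stated denominator counts patients with unknown outcome as event-free and departs from the rule in SAP 6.15.5.1. At an assumed 2% to 10% untested, a true 10% reads 9.8% to 9.0%. The ratio between arms is biased only where the shares differ, in a direction that depends on which arm has more untested patients.

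Lipids are the most plausible place. That conclusion rests on the 30 days running from the last dose. If the treatment period meant the full 16 weeks whatever the drug status, the Week 12 sample would count and this route would close. The event definition names only the treatment period, while the section's opening adds the off-drug days; the working uses the wider window. The hepatic threshold analyses and the efficacy results are untouched.

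**What to change.** In SAP 6.15.3, add to both number-at-risk definitions: *and at least 1 postbaseline value of that analyte in the analysis period*. Let SAP 6.15.4 inherit the same denominator for consistency, although little will change there. If the compound-level standards already impose the condition, 6.15.3 should say so.

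The cost is one sentence and a denominator filter, with no change to data collection. Denominators become slightly smaller and percentages slightly higher.
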